11 ADVERSE EVENTS

The Investigator, or a delegated researcher, is responsible for the detection and documentation of adverse events that may be related to participating in the study and that meet the criteria and definitions detailed below.

11.1 DEFINITIONS

An **adverse event** (AE) is an untoward medical occurrence in a study participant. An **adverse reaction** (AR), in the context of this study, is any untoward and unintended response which is related to the ketogenic diet administered to that participant.

A serious adverse reaction (SAR) is any AR that:

- results in death of the clinical trial participant; is life threatening*;
- requires in-patient hospitalisation or prolongation of existing hospitalisation;
- results in persistent or significant disability or incapacity;
- consists of a congenital anomaly or birth defect;
- results in any other significant medical event not meeting the criteria above.

A suspected unexpected serious adverse reaction (SUSAR) is any AR that is classified as serious and is suspected to be caused by the ketogenic diet.

*Life-threatening in the definition of an SAE or SAR refers to an event where the participant was at risk of death at the time of the event. It does not refer to an event which hypothetically might have caused death if it were more severe.

^Any hospitalisation that was planned prior to randomisation will not meet seriousness criteria. Any hospitalisation that is planned post randomisation will meet the seriousness criteria unless it does not constitute an untoward medical occurrence (e.g. cosmetic elective surgery, social and/or convenience admission, etc.).

11.2 IDENTIFYING AEs AND ARS

All AEs and ARs will be identified from the time a participant signs the consent form to take part in the study until the completion of study follow-up.

11.3 RECORDING AEs AND ARS

AEs will be recorded as part of the outcome measures in the study CRF. There is no requirement to complete an additional AE form. When an AE occurs, it is the responsibility of the Investigator to review all documentation (e.g. hospital notes, laboratory and diagnostic reports) related to the event. To the extent the CRF permits, the Investigator will record relevant safety information in the CRF.

Any adverse reaction (AR) to the ketogenic diet that meets seriousness criteria (see section 9.1) will be recorded and reported in the study CRF and will also be recorded on an ACCORD SAE form, which will then be sent to the Sponsor via email ([contact]).

Pre-existing medical conditions (i.e. existed prior to informed consent) should be recorded as medical history and only recorded as AEs/ARs if medically judged to have unexpectedly worsened during the study. Events that are consistent with the expected progression of underlying disease should not be recorded as adverse events.

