2.3 PRIMARY OBJECTIVES

- Recruit 25 patients with bipolar disorder [BD] who are euthymic at time of presentation.
- Support the introduction of a KD over an 8-week period and determine the most appropriate diet formulation and means of introduction and maintenance in this group.
- Investigate adherence rates with a KD intervention in this patient group and the level of support required to introduce KD successfully.
- Investigate evidence of short-term metabolic changes [from blood metabolomic and brain imaging studies] associated with KD consistent with underlying study hypothesis for mechanism of action.
- Report any adverse effects associated with use of KD in this patient group.
- Explore the feasibility and acceptability of the KD to patients and clinicians.
- Explore feasibility and acceptability of study processes for a future trial e.g. recruitment procedures, monitoring and outcome assessments.
- Document the range and variability of outcome parameter values (to inform future clinical trial design).
- Investigate preliminary signals of efficacy on mood instability, quality of life and functional outcomes in this patient cohort (in a before-after assessment).

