2.6 SECONDARY OUTCOME MEASURES

- Mood stability measured by the Affective Lability Scale (ALS18) and Beck Depression Inventory (BDI) at baseline and at 8-week followupHypomania/mania symptoms measured using the Young Mania Rating Scale (YMRS) at baseline and 8-week follow up
- Glucose/ketone ratio measured using ketomojo devices daily throughout the 10 week study period
- Identification of specific metabolic changes in glucose, ketones and TCA metabolites associated with the KD that are predicted by the study

- hypothesis, measured using serum and brain MRI measures at baseline and week 8
- Mood, energy, speed of thought, impulsivity and anxiety measured using visual analogue scales from 1-100 at daily ecological momentary assessments during the 10-week study period
- Episodes of bipolar depression and hypomania/mania occurring during the study period assessed by repeat MINI Neuropsychiatric assessment at baseline and week 8.
- Sleep duration and circadian activity/rest rhythmicity parameters assessed by actigraphs throughout the 10-week period (to include 2 weeks of stepping down the diet).

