4.2 INCLUSION CRITERIA

- Meet the DSM-4 diagnostic criteria for bipolar disorder type 1 or 2, for at least 1 year, assessed using the MINI Neuropsychiatric Interview
- Clinically stable and currently euthymic, defined as 3 months with no major mood episodes (major depression lasting at least 2 weeks or hypomania/mania lasting at least 1 week), assessed using the MINI Neuropsychiatric Interview
- Aged 18 to 70 years (upper age limit set due to increased risk of age-related changes over 70 making interpretation of brain imaging more difficult – we will aim to increase the upper age limit in a full clinical trial).
- Able to provide informed consent to take part in the study
- Able to speak, read and understand English to a level whereby they can understand the participant information sheet (PIS). (This is due to the

practicalities of implementing translation services for such a small pilot study, however we would hope to include non-English speaking participants in a future larger clinical trial).

· Currently living in Scotland

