11.4.2 Assessment of Seriousness

Subsequent to the assessment causality, the Investigator will make an assessment of seriousness as defined in Section 9.1.

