11.4.3 Assessment of Severity

The Investigator will make an assessment of severity for each SAR, and record this on the ACCORD SAE form according to one of the following categories:

Mild: an event that is easily tolerated by the participant, causing minimal discomfort and not interfering with every day activities.

Moderate: an event that is sufficiently discomforting to interfere with normal everyday activities.

Severe: an event that prevents normal everyday activities.

Note: the term 'severe', used to describe the intensity, should not be confused with 'serious' which is a regulatory definition based on participant/event outcome or action criteria. For example, a headache may be severe but not serious, while a minor stroke is serious but may not be severe.

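### The adverse-event rules leave mood relapse open to omission, define seriousness only for diet-related reactions and grade severity only for serious ones, so the safety description may be incomplete

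*Protocol*

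**What the plan says.** Section 2.3 makes safety one of the primary objectives: "Report any adverse effects associated with use of KD in this patient group". Section 11.2 has all adverse events (AEs) and adverse reactions (ARs) identified from consent to the end of follow-up, and 11.3 has AEs recorded in the case report form (CRF).

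Section 11.3 then narrows what counts. A pre-existing condition is "only recorded as AEs/ARs if medically judged to have unexpectedly worsened during the study". The next sentence adds: "Events that are consistent with the expected progression of underlying disease should not be recorded as adverse events". Neither sentence mentions mood episodes.

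On classification, 11.1 attaches the seriousness criteria to ARs only. It gives no definition of a serious adverse event (SAE), although its footnote and the heading of 11.4 use the term. Section 11.4.2 fixes the order: "Subsequent to the assessment causality, the Investigator will make an assessment of seriousness". The opening of 11.4 lists seriousness, causality, severity and expectedness as things to be assessed and makes the investigator responsible for assessing every AE. Section 11.4.3 is narrower: "The Investigator will make an assessment of severity for each SAR".

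A footnote in 11.1 states: "Any hospitalisation that was planned prior to randomisation will not meet seriousness criteria". The study has one arm and no randomisation.

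**The concern.** Section 1.1 describes episodes of depression and mania as the course of bipolar disorder. An investigator can therefore reasonably regard a relapse on the diet as expected progression and not record it. Such an event never reaches the causality assessment in 11.4.1. With no control arm, attribution would have been settled by a recording rule and not by judgement of the case.

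Destabilisation is an obvious psychiatric harm to look for in people selected for stability. Section 1.2 gives learning about adverse effects in this population as a reason for running the pilot, and 6.1 makes consideration of early stopping depend on significant adverse effects becoming apparent. Two investigators applying 11.3 in opposite ways would produce harm data that cannot be interpreted.

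The other two gaps affect the remaining harms. A serious event judged unrelated has no label of its own, and the tolerability problems most likely to occur have no prescribed severity grade.

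**Working it through.** The protocol gives no event rate or safety precision target, so there is no figure to reproduce. The check sets the passages side by side and adds one illustration.

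**1. Is a mood relapse recorded as an AE?**
- Against recording: the progression sentence in 11.3, read with the description of the illness in 1.1.
- For recording: the preceding sentence in 11.3, which keeps unexpected worsening, read with 4.2, which requires participants to be "Clinically stable and currently euthymic, defined as 3 months with no major mood episodes". A new episode after that can be called unexpected.
- Result: both readings are available and nothing in section 11 chooses between them.

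**2. What class does a serious but unrelated event have?**
- 11.1 defines seriousness for ARs; 11.4.2 puts it after causality; 11.5 sends only serious adverse reactions (SARs) and SUSARs to the sponsor within 24 hours.
- Result: the event is an AE in the CRF. It has no defined serious category, although the term SAE is used.
- The cross-references in 11.3 and 11.4.2 do not help. They send the reader to section 9.1, which is Personal Data; the criteria are in 11.1.

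**3. Which events get a severity grade?**
- The opening of 11.4 reads as covering AEs generally; 11.4.3 names SARs only.
- The effects expected in 3.3 (such as fatigue, irritability and constipation) are described there as typically mild, so they would seldom be SARs.
- Result: the two passages conflict, and under 11.4.3 the effects expected to be common go ungraded.

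**4. Does other data collection fill the gap?**
- Section 2.6 lists as an outcome: "Episodes of bipolar depression and hypomania/mania occurring during the study period assessed by repeat MINI Neuropsychiatric assessment at baseline and week 8". It also lists ALS-18, BDI, YMRS, daily ratings and actigraphy.
- Section 3.4.2 allows the follow-up visit in week 6, 7 or 8 and continues daily ratings and actigraphy to week 10. No later diagnostic interview is scheduled, so roughly 10 − 8 = 2 to 10 − 6 = 4 weeks, including the cessation period, have none.
- Result: mood is well measured, but none of these outcomes carries a causality, seriousness or severity judgement. Sections 2.5 and 2.6 list no AE outcome, although 11.3 treats AEs as part of the outcome measures.

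**5. Illustration of size.** N = 25 (section 4.1). The 10-week relapse rate p is an assumption. Expected events = 25p; chance of at least one = 1 − (1 − p)^25.

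| Assumed p | Expected events | Chance of at least one |
|---|---|---|
| 5% | 1.25 | 72% |
| 10% | 2.5 | 93% |
| 20% | 5 | 99.6% |

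If every relapse were treated as expected progression, the AE table would show 0/25 for mood episodes. The exact two-sided 95% upper limit for 0/25 is 1 − 0.025^(1/25) = 13.7%, below the 20% at the top of the assumed range. The protocol plans no such interval (10.2 is descriptive); the limit only shows how a reader might take a zero.

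**The case against.** A reader might infer that the protocol drops mood relapses. It does not say so: 11.3 never names them and keeps unexpected worsening as recordable. The defect is ambiguity.

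A reader might also infer that the primary safety objective cannot be met. That does not follow. The objective is descriptive and sets no rate or severity profile, and AEs are to be identified, recorded and judged for causality. Mood episodes would be reported as outcomes under 2.6, so a zero in the AE table would not stand alone.

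Nor is the MINI the only other source. BDI, YMRS, daily ratings and actigraphy are collected, app data are reviewed at least weekly (3.4.3), the dietitian is in weekly contact, and participants can email adverse effects or contact a study psychiatrist (3.3).

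It would also be wrong to say that unrelated serious events never reach the sponsor. Section 11.6 requires quarterly safety reports to the sponsors' office from CRF data. The narrow 24-hour route in 11.5 has a stated rationale, that the procedures are well established. The order in 11.4.2 does not by itself bar assessing seriousness for unrelated events, and 11.4.1 sets a low threshold for possible relation.

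All of this limits the point without removing it. The low causality threshold helps only if the event is recorded. The quarterly report would carry a serious unrelated event without a defined serious label. The rationale in 11.5 sits uneasily with 1.1, which says negative effects of the diet have not yet been explored in bipolar disorder.

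**Conclusion.** The concern holds as a defect in the recording and classification rules. Section 11.3 permits, but does not order, omission of mood episodes and psychiatric admissions before causality is judged. Sections 11.1 and 11.4.2 leave serious unrelated events without a class, and 11.4.3 conflicts with the opening of 11.4 on severity. The consequence is an AE description that may be incomplete and biased towards few harms, for an objective the protocol calls primary.

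The size cannot be fixed from the document. The range of 1.25 to 5 events in 25 rests on an assumed 5% to 20% relapse rate, and their loss from the AE record rests on the further assumption that all are classed as expected progression. The textual findings need neither assumption. The reference to randomisation is a minor leftover, but it leaves the planned-hospitalisation rule without a usable dividing line.

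**What to change.** Amend section 11 as follows; no treatment or clinical management rule changes.

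- **11.3:** state that new or worsened mood episodes, suicidal ideation or acts, and psychiatric admissions, from consent to the end of follow-up, are recorded as AEs whatever their presumed cause.
- **11.1 and 11.4:** define SAE, and assess seriousness for every AE independently of causality. List SAEs in the quarterly report that 11.6 already requires; the 24-hour route in 11.5 can stay as it is.
- **11.4.3:** apply the existing three severity grades to all AEs, in line with the opening of 11.4.
- **11.1:** replace randomisation with consent in the planned-hospitalisation footnote.
- **11.3 and 11.4.2:** correct the cross-reference from 9.1 to 11.1.

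The cost is amendment wording, a few more CRF lines completed at existing contacts, and a longer AE listing. The change is best made before data collection, because events left unrecorded may not be reliably reconstructed later.

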11.4 ASSESSMENT OF AEs, SAEs, ARs, SARs and SUSARs

Seriousness, causality, severity and expectedness will be assessed by the PI. The Investigator is responsible for assessing each adverse event. The CI may not downgrade an event that has been assessed by an Investigator as a SAR or SUSAR, but can upgrade an AR, SAR or SUSAR if appropriate.

11.4.1 Assessment of Causality

The Investigator will make an assessment of whether an AE is likely to be related to the administration of the ketogenic diet (and therefore be considered an AR) according to the definitions below.

- Unrelated: Where an event is not considered to be related to the administration of the ketogenic diet.
- Possibly Related: The nature of the event, the underlying medical condition, concomitant medication or temporal relationship make it possible that the AE has a causal relationship to the administration of the ketogenic diet in this study.

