The participant will also attend the Royal Infirmary of Edinburgh for an MR spectroscopy (a type of brain scan) (around 1 hour). This is non-invasive and will not require injection of any substances. This will allow us to measure metabolic markers in the brain and compare these before and after the intervention. Please see imaging data analysis section for more information. All standard imaging service procedures will be followed.

Participants may find MRI brain scans anxiety provoking and may experience claustrophobia during the scans. The research team will ensure that the procedure is explained to participants, so they know what to expect. The research co-ordinator will attend this appointment with participants if necessary and appropriate. If any incidental findings occur, the participants GP will be informed.

Participants will be fully informed about what all the above assessments and interventions entail in both the PIS, and through discussions with the research team. The research team will spend time ensuring participants fully understand all aspects of the study, and how to use all the devices before they are expected to use them themselves. They will also be contactable by participants throughout the study.

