3.4.2 FOLLOW UP ASSESSMENTS

Participants will attend for repeat venepuncture and brain imaging in week 6, 7, or 8 of the 8-week intervention period. They will need to be fasted prior to this and will follow the same process as the baseline venepuncture and brain imaging. A psychiatrist will then repeat the baseline questionnaires and physical parameters as detailed above. The dietitian will clarify with them if they plan to continue the KD. If they do plan to continue the dietitian will provide further advice about how to do this. The dietitian will also be available for a further 4 weeks following the end of the 10-week study period, to provide ongoing advice and support if participants plan to continue the KD. We will aim for all follow up assessments to take place during one appointment.

Participants will be asked to monitor glucose and ketone measurements every day, wear their actigraph device, and record mood daily for the full 10-week study period. This will apply if they decide to stop the diet after 8 weeks or if they have decided to continue the diet. This will allow us to see if there are any changes in these parameters related to stopping the diet.

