11.5 REPORTING OF SARs/SUSARs

As this trial is a non-CTIMP and involves procedures and interventions that are very well established in the medical community, with extensive information available regarding risks, only serious adverse reactions (SARs) and Suspected Unexpected

Serious Adverse Reactions (SUSARs) related to the ketogenic diet administration, will be onward reported to the Sponsor.

Once the Investigator becomes aware that a ketogenic diet related SAR/SUSAR, has occurred in a study participant, the information will be reported to the ACCORD Research Governance & QA Office within 24 hours. If the Investigator does not have all information regarding an event, they should not wait for this additional information before notifying ACCORD. The ACCORD SAE report form will be used to submit the event report, and can be updated when the additional information is received.

The SAE form will be transmitted by fax to ACCORD on [name] or may be submitted by hand to the office or sent via email to [contact]. Only forms in a pdf format will be accepted by ACCORD via email.

Where missing information has not been sent to ACCORD after an initial report, ACCORD will contact the investigator and request the missing information.

All reports sent to ACCORD and any follow up information will be retained by the Investigator in the Investigator Site File.

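### Relatedness is judged only against the ketogenic diet, so a serious event caused by a study procedure is coded Unrelated and gets no prompt individual report

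*Protocol*

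**What the plan says.** Section 11 of the protocol opens by making the investigator responsible for detecting and documenting "adverse events that may be related to participating in the study and that meet the criteria and definitions detailed below". The sub-sections that follow ask only about the diet:

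- **11.1** defines an adverse reaction as "any untoward and unintended response which is related to the ketogenic diet administered to that participant". Serious adverse reactions and SUSARs are subsets of this.
- **11.3** sends an SAE form to the sponsor only for a reaction to the diet that meets the seriousness criteria. All adverse events are recorded on the CRF.
- **11.4.1** has two categories. The first is "Unrelated: Where an event is not considered to be related to the administration of the ketogenic diet"; the second, Possibly Related, also refers to administration of the diet.
- **11.5** limits 24-hour reporting to serious reactions "related to the ketogenic diet administration, will be onward reported to the Sponsor".
- **11.6** provides quarterly safety reports, drawn from CRF data, to the ACCORD office, which acts for the co-sponsors.

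Elsewhere the protocol foresees harm from procedures. Section 3.4.1 mentions discomfort, needle distress and bruising from blood tests, and says of the scans: "Participants may find MRI brain scans anxiety provoking and may experience claustrophobia during the scans". Section 3.4.2 continues daily monitoring through weeks 9 and 10 and explains: "This will allow us to see if there are any changes in these parameters related to stopping the diet".

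The seriousness definitions in 11.1 also contain the rule "Any hospitalisation that was planned prior to randomisation will not meet seriousness criteria".

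**The concern.** The opening of section 11 concerns harm from taking part. The operative definitions concern harm from the diet. In a study whose procedures include two MRI scans, two venepunctures and daily finger-pricks, these are not the same thing.

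Two consequences follow. A serious injury caused by a procedure has no prompt, individual route to the sponsor. And the causality code loses information: harm done by the study's own tests and illness that merely coincides with the study receive the same label. Section 2.3 makes the feasibility and acceptability of monitoring and outcome assessments a primary objective, with a future trial in view, so the safety data should be able to show what those assessments cost participants.

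The step-down raises a related doubt. If administration is read narrowly, an effect of coming off the diet is not an effect of its administration. If it is read broadly, it is. The protocol does not say which, so two investigators could code the same event differently.

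The planned-hospitalisation rule is a separate slip in the same definitions. It is dated from randomisation, but under section 3.3 every participant receives the diet.

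**Working it through.** The protocol states no figure on this point, so the check is to follow three events through section 11 and then count the planned exposure.

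**Event A: serious, caused only by the baseline scan or blood draw.**
1. Section 11.2 starts the adverse-event window at consent, and 3.4.1 places these procedures after consent and before the diet. The event is an adverse event and goes on the CRF (11.3).
2. Under 11.4.1 the diet has not begun, so Unrelated is the only category available.
3. It is therefore not an adverse reaction under 11.1. The seriousness criteria there are attached to reactions only, so it cannot become a SAR or SUSAR. Severity grading in 11.4.3 is likewise asked for SARs only.
4. No SAE form (11.3) and no 24-hour report (11.5) follow.
5. Its CRF record feeds the next quarterly report (11.6), coded Unrelated.

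**Event B: serious, caused only by a finger-prick, or by the scan or blood draw in weeks 6 to 8.** The participant is now on the diet, but the cause is the procedure. Steps 2 to 5 give the same result.

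**Event C: serious, caused by stepping down from the diet in weeks 9 and 10.** The wording points two ways:
- Read literally, administration excludes withdrawal, and the event is Unrelated.
- Section 3.3 describes the step-down as part of the diet intervention, 11.1 speaks of a response related to the diet that was given, and 11.4.1 lets timing support Possibly Related. On that reading the event is a SAR and is reported within 24 hours.

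The text does not decide between the two.

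**Planned exposure.** Inputs: 25 participants (4.1); scan and venepuncture at baseline and once in weeks 6 to 8 (3.4.1, 3.4.2); daily glucose and ketone testing for 10 weeks (3.4.1, 3.4.2); 2-week step-down (3.3).
- Scans: 25 × 2 = 50, of which 25 × 1 = 25 precede the diet.
- Venepunctures: 25 × 2 = 50, of which 25 precede the diet.
- Finger-prick days: 25 × (10 × 7) = 25 × 70 = 1,750.
- Step-down share of the monitored period: 14 / 70 = 20%.

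These figures assume full recruitment and no drop-out. They count exposures, not events.

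**The case against.** The strongest defence is that the narrow scope is a reasoned choice. Section 11.5 justifies it by the study being a non-CTIMP with well-established procedures and interventions. The safety objective in 2.3 is to report adverse effects of the diet, and the causality question matches it. For a bruise or a panic in the scanner, unrelated to the diet is a true answer. Most of the foreseen procedure harms are minor and would not be reported individually under any definition. Procedure burden is also studied through compliance outcomes (2.5) and the process evaluation (3.7). All of this stands, and it limits the weight of the point. It does not supply a prompt route for the rare serious procedure injury, nor a code that distinguishes it.

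Three stronger readings are tempting, and the protocol does not support them:

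- *Such events never reach the sponsor.* All adverse events go on the CRF, and 11.6 sends quarterly CRF-based reports to the office acting for the co-sponsors. What is lost is the individual and prompt report. The word only in 11.5 sits awkwardly with 11.6.
- *The step-down would show no reactions by definition.* Event C shows that this is one reading, not a forced one. Some participants may also continue the diet in those weeks, and the monitoring in 3.4.2 yields outcome data whatever the adverse-event coding.
- *Section 11 contradicts itself.* Its opening sentence is limited to events meeting the definitions that follow, so this is a mismatch of scope.

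**Conclusion.** The point holds in limited form. An event caused solely by a study procedure must be coded Unrelated; this follows directly from 11.1 and 11.4.1. If serious, it gets no SAE form and no 24-hour report, and may wait up to about a quarter before it appears in the report under 11.6, with a code that does not separate it from coincidental illness. For step-down effects the finding is ambiguity, with a risk of inconsistent coding.

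The size can be given only as exposure: 50 scans, 50 venepunctures and 1,750 finger-prick days, assuming 25 completers, and 20% of monitored time in the step-down. The protocol gives no rate of procedure-related events, so the number misclassified cannot be estimated, and serious ones may well be none. The point bears on safety classification and prompt reporting; it does not undermine the feasibility outcomes. It should be corrected because the remedy is small. The reference to randomisation is a plain error, independent of the causality question, and adds nothing to its weight.

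**What to change.** 1. In 11.1, 11.3 and 11.4.1, define related as related to the ketogenic diet, including its introduction and step-down, or to a study procedure (MRI, venepuncture, finger-prick testing).
2. Add one CRF field recording which of these applies, so that diet and procedure events can be told apart.
3. Apply the same definition to SAR and SUSAR reporting in 11.5, and reconcile 11.5 with 11.6 on what goes to the sponsor individually and what goes in the quarterly report.
4. In the planned-hospitalisation rule of 11.1, replace randomisation by signature of the consent form, the reference point already used in 11.2 and 11.3.

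The cost is wording in a few sub-sections and one CRF field. The downside is that a few more events will be classed as related, with possibly an extra report to the sponsor.
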